6.3 PRIMARY VIROLOGIC SAFETY ANALYSIS

Are HIV-1 RNA levels equivalent among HIV-infected patients on HAART versus those not on HAART following vaccination between baseline and timepoint X?

The statistical analysis assumes that an equivalence test will be used, and that no more than 5% of HIV-infected individuals would experience a $\geq 0.5 \log_{10}$ (the range of biologic variation) increase in HIV-1 RNA levels within a week following vaccination or at subsequent time-points. The primary goal of this statistical safety analysis is to determine whether the fraction of patients experiencing a $\geq 0.5 \log_{10}$ increase in HIV-1 RNA levels *at any time within the first week* and up to 1 year following the first immunization, may be considered equivalent between those HIV-infected individuals receiving HAART and those not on HAART following receipt of quadrivalent HPV vaccine. Time-point 1 comparisons of changes in the peak HIV-RNA levels from day 1 between Cohort 1 and 2 during any of the evaluations during the first week (see below) will be considered as the most important primary evaluation for this equivalence study and will be the basis for sample size determination. Another primary evaluation will be based on determining the equivalence of the fractions with day 7 vs. day 1 levels $\geq 0.5 \log_{10}$ (the range of biologic variation) increase in HIV-1 RNA levels between the two cohorts.

Equivalence tests can require a tremendous number of subjects in order to allow only a small interval of difference to be interpreted as equivalent. In order to allow for the test to be done with a moderate number of patients, the two vaccine cohorts will be considered equivalent if the fraction of vaccine recipients in one cohort who have an HIV-1 RNA level increase $\geq 0.5 \log_{10}$ is within 10% of that of the other cohort. Thirty-five patients are required per arm within each HIV-infected cohort, to have 73% power to document this level of equivalence. Formally stated, 35 patients per arm was selected as the sample size in order to allow a single two-group t-test of proportions with a one-sided 0.10 significance level to have 73% power to reject the null hypothesis that the two cohorts are not equivalent with respect to the fraction of patients experiencing a $\geq 0.5 \log_{10}$ increase in HIV-1 RNA levels *at each individual time comparison--the maximum increase within the first week* and up to 1 year following the first immunization.

Timepoints for HIV-1 RNA Level Analysis: Comparison between Recipients in HIV-Infected Cohorts 1 and 2:

- Timepoint 1 Day 1 vs. Day 3 or Day 7 (immediately s/p vaccination) (*primary*)
- Timepoint 2 Day 1 vs. mos 1 (1mos s/p 1 vaccination)
- Timepoint 3 Day 1 vs. mos 3 (1mos s/p 2 vaccinations)
- Timepoint 4 Day 1 vs. mos 7 (1mos s/p 3 vaccinations)
- Timepoint 5 Day 1 vs. mos 12 (6mos s/p 3 vaccinations)

Within each cohort, the change in \log_{10} HIV-1 RNA levels will be determined between day 1 and day 7 and will be evaluated to see if the values at the two time points are not statistically different from one another. HIV-1 RNA levels below the lower limits of detection (50 copies/ml) will be expressed as 1.69 \log_{10} on a logarithmic scale equivalent to 49 copies/ml. With a minimum of 27 patients in each cohort of HIV-infected individuals, there is at least 95% power to detect a change from day 1 to day 7 with an effect size of 1 SD and a 0.025 two-sided alpha level test (0.05/2cohorts) after allowing for a Bonferroni adjustment.

In addition, as a secondary evaluation, comparison of changes in HIV-1 RNA levels will also be done among the two cohorts from day 1 to day 7, and months 1, 3, 7 and 12 in order to assess if the change in level may have some association with the cohort in which the patient is enrolled. This evaluation will be considered exploratory for all comparisons and timepoints.

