1 INTRODUCTION

1.1 STUDY OBJECTIVES

The **primary** objectives of this study are to:

- Assess the immunogenicity and safety of the quadrivalent human papillomavirus (types 6, 11, 16, 18) 3

The **secondary** objectives of this study are to:

- Determine whether there are differences in HPV vaccine immunogenicity between HIV-infected and HIV uninfected age-matched controls.
- Determine whether there are differences in HPV vaccine immunogenicity between HIV-infected patients receiving highly active antiretroviral therapy (HAART) and those not receiving HAART with similar CD4 and viral load parameters at entry.
- Determine whether HPV vaccination alters HIV-1 RNA levels.
- Investigate the impact of CD4 count and HIV-1 RNA levels on HPV vaccine immunogenicity.
- Characterize HPV DNA positivity by oral/buccal and anogenital swabs at baseline in the study cohort populations.
- Characterize HPV and HIV knowledge and risk and sexual behaviors in the study cohort populations.

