1.2.6 Rationale for Study Cohort Population

This study will be conducted in both HIV-infected females and males 12-26 years of age. Since the risk of HPV acquisition is intensified during adolescence and young adulthood because of risk-taking and exploratory behaviors and because of the well-documented co-morbidities associated with sexually acquired HPV in individuals with HIV infection, both males and females are included in the study. It is anticipated that Cohort 1 will be comprised primarily (but not exclusively) of sexually naïve pre-adolescents and adolescents infected with HIV vertically or by transfusion early in life that have experienced successful immune reconstitution and viral load reduction on HAART therapy (i.e. CD4 count ≥ 350 cells/mm³ and HIV-1 RNA levels $\leq 20,000$ copies/ml). This population represents an ideal one to investigate vaccine immunogenicity given the high likelihood of HPV acquisition following the initiation of sexually activity.

It is anticipated that Cohort 2 will be comprised primarily (but not exclusively) of adolescents and young adults with sexually acquired HIV infection that have no current indication for HAART therapy according to current USPHS Treatment Guidelines (i.e. CD4 count ≥ 500 cells/mm³ and HIV-1 RNA levels $\leq 20,000$ copies/ml).⁹⁸ These individuals represent a unique population to assess HPV vaccine immunogenicity and safety that parallels populations in developing countries with little or no access to antiretroviral treatment where there is a high burden of prevalent HPV and HIV disease. Both Cohorts 1 and 2 will permit assessment of whether HPV vaccination is associated with alterations in HIV-1 RNA levels and if observed, whether alterations are mitigated in the presence of HAART. In addition, both HIV-infected cohorts will allow investigation of the impact of CD4 count and HIV-1 RNA levels on HPV vaccine immunogenicity.

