5.2 RESPONSE CRITERIA

The primary focus of this clinical study is immunogenicity as measured by development of and change in antibody titers to the four HPV types within the quadrivalent HPV vaccine. HPV-specific antibody titers will be measured at baseline and s/p receipt of 1, 2 and 3 doses of vaccine, in addition to serial, longitudinal monitoring of HPV titers every 6 months following completion of the vaccination series for a total of 4 years to assess antibody titer decay and duration of immunogenicity.

The only clinical outcomes that will be monitored for response are for safety criteria, as this study is not statistically powered to assess vaccine efficacy even on a preliminary level in the currently defined study cohort populations. Safety will be monitored through the use of Vaccination Report Card (VRC) Surveillance for Adverse Vaccine Experiences to assess local injection site and systemic reactions to vaccination, in addition to monitoring of laboratory values. In HIV-infected study subjects, this safety assessment also includes virologic parameters to ensure that HPV VLP vaccination is not associated with upregulation of viral replication and increased HIV-1 RNA levels.

Research assessments that will be evaluated in a descriptive observational manner include:

- Cross-sectional characterization of HPV DNA positivity by oral/buccal and anogenital swabs at baseline in the study cohort populations.
- Longitudinal changes following vaccination in:
 - lymphocyte proliferation assays to HPV and HIV antigens
 - cytokine induction and profile
 - activation and proportional representation of lymphocyte subset populations (HIV-infected patients only)
- Cross-sectional and longitudinal characterization of HPV and HIV knowledge and risk and sexual behaviors in the study cohort populations.

Specific statistical approaches to the primary immunogenicity and virologic safety analyses, and secondary analyses of HIV-related parameters (use of HAART, CD4 cell count and HIV-1 RNA levels) on vaccine immunogenicity are outlined in complete detail in the statistical section 5.4.

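### The virologic safety tests designated primary compare two vaccinated cohorts, so they cannot show whether vaccination raises HIV-1 RNA; the one planned test that could is unlabelled, has no margin and stops at day 7.

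*Combined protocol and SAP*

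**What the plan says.** Section 1.1 lists among the secondary objectives: "Determine whether HPV vaccination alters HIV-1 RNA levels". Section 5.2 gives the purpose of the virologic safety assessment as "to ensure that HPV VLP vaccination is not associated with upregulation of viral replication and increased HIV-1 RNA levels". Both ask what happens to HIV-1 RNA after vaccination.

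Section 6.3 asks a different lead question: "Are HIV-1 RNA levels equivalent among HIV-infected patients on HAART versus those not on HAART following vaccination between baseline and timepoint X". Its stated goal is to decide whether the fractions with a rise of at least 0.5 log10 "may be considered equivalent between those HIV-infected individuals receiving HAART and those not on HAART following receipt of quadrivalent HPV vaccine". The week-1 comparison of Cohort 1 with Cohort 2 "will be considered as the most important primary evaluation for this equivalence study and will be the basis for sample size determination". A second primary evaluation is also between cohorts: "Another primary evaluation will be based on determining the equivalence of the fractions with day 7 vs. day 1 levels". The design assumes that "no more than 5% of HIV-infected individuals would experience a" rise of that size. It sets a 10-point margin between cohorts and claims 73% power with 35 per cohort at one-sided 0.10.

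The same section then plans a test within each cohort of the change in log10 HIV-1 RNA from day 1 to day 7. This has its own alpha (0.025 two-sided) and a power statement (at least 95% for a 1 SD change with 27 patients). It is described apart from the evaluation named secondary, but it is not called primary. Months 1, 3, 7 and 12 appear only in comparisons between the two cohorts.

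**The concern.** Cohorts 1 and 2 receive the same vaccine on the same schedule. Their difference can say whether HAART changes the response to vaccination; it cannot say whether there is a response. Section 1.2.6 puts the questions in the natural order: first whether vaccination is associated with altered HIV-1 RNA and, if so, "whether alterations are mitigated in the presence of HAART". Section 6.3 makes the conditional second question primary and bases the sample size on it.

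Sections 8.3 and 8.4 expect any rise to be smaller on HAART. A difference between cohorts is therefore the pattern of harm the protocol anticipates, while similarity is compatible with no rise or with a rise in both. At stake is whether the result reported as the primary virologic safety finding can be read as evidence about the vaccine at all.

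**Working it through.** **Inputs (section 6.3).** n = 35 per cohort; assumed event rate 5% in each; margin 0.10; one-sided alpha 0.10, so z = 1.2816. An event is a rise of at least 0.5 log10.

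**1. Reproduce the plan's power.** The standard error of the difference is sqrt(2 × 0.05 × 0.95 / 35) = 0.0521. Power = Φ(0.10/0.0521 − 1.2816) = Φ(0.638) = 73.8%; a noncentral t with 68 df gives 73.4%. The stated 73% reproduces as the power of one one-sided test. Two one-sided tests (TOST), which a symmetric criterion would need, give 2 × 0.738 − 1 = 47.6%.

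**2. Change the common rate.** The power formula depends on the common rate p only through p(1 − p), so p and 1 − p give the same answer. Exact binomial enumeration with the unpooled Wald standard error gives the chance of declaring equivalence:

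| Rate in both cohorts | One-sided test | TOST |
|---|---|---|
| 5% | 74.7% | 49.5% |
| 20% | 42.2% | 0.9% |
| 80% | 42.2% | 0.9% |
| 95% | 74.7% | 49.5% |

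The rates other than 5% are illustrations, not forecasts. The lower values at 20% and 80% come from larger binomial variance, not from any sensitivity to harm: a failure there means only that the cohorts were not shown to be alike.

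**3. The within-cohort test.** Paired t, two-sided alpha 0.025, noncentrality d × sqrt(n). With n = 27, critical t = 2.379:

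- d = 1 SD: noncentrality 5.20, power 99.6% (consistent with the stated minimum of 95%)
- d = 0.5 SD: noncentrality 2.60, power 59%
- d = 0.25 SD: noncentrality 1.30, power 16%

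This test does respond to a rise. It addresses mean change rather than the fraction with a 0.5 log10 rise, and a non-significant result is a weak basis for reassurance when the change is half an SD or less.

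**4. What a direct estimate would deliver.** Clopper-Pearson one-sided 95% upper limits:

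| Events | Upper limit |
|---|---|
| 0/35 | 8.2% |
| 1/35 | 12.9% |
| 2/35 | 16.9% |
| 0/70 | 4.2% |
| 1/70 | 6.6% |

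A single cohort cannot exclude a 5% rate even with no events; the pooled cohorts can, but only with none.

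**5. Are the samples scheduled?** Sections 6.3 and 7.5.1 rely on HIV-1 RNA at days 1, 3 and 7. Appendix 2A has no HIV-1 RNA at month 0 day 1 and no day 3 or day 7 column; the vaccine-visit laboratory list in section 3.5.1.2 omits HIV-1 RNA. Appendix 2A does show it at screening and at months 1, 2, 3, 6, 7 and 12.

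**The case against.** The strongest reply is that section 6.3 does more than compare cohorts. It includes a within-cohort test with its own alpha and power, which would detect a large rise in either cohort. This stands. A reader might infer that the plan has no means of detecting a rise; the documents do not support that. The limits of the test are its unstated rank, its lack of a margin, and its restriction to the first week.

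A reader might also infer that equal harm in both cohorts would usually pass as equivalence. That is not supported either: at a common rate of 20% the one-sided test passes 42% of the time and TOST 0.9%. The defect is that neither a pass nor a failure indicates whether HIV-1 RNA rose.

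The comparison does answer the question that section 6.3 itself poses, and it bears on mitigation by HAART, a stated purpose in section 1.2.6. The fault is a mismatch with sections 1.1 and 5.2. One could treat Cohort 1 as a near-zero reference, but the plan does not say so, sets no condition on Cohort 1's rate, and admits patients to it with up to 20,000 copies/ml.

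The off-treatment criterion for HIV-1 RNA (section 3.7), the accrual stopping rule (section 6.7) and the monitoring in section 7.5.1 also watch absolute values. They are safeguards, not estimates of a vaccine effect.

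Finally, there is no unvaccinated HIV-infected group, so a before/after estimate cannot fully separate vaccine effect from natural drift. This also stands, and limits any remedy within the present design.

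**Conclusion.** The concern holds for the evaluations designated primary, including the one that sets the sample size. They have the same chance of success at a 5% and a 95% rise rate in both cohorts (74.7% one-sided, 49.5% TOST), and nothing tests the 5% ceiling. These figures rest on the plan's own n, margin and alpha, and on a Wald test with unpooled variance, the form that reproduces the stated power. The 5%/95% identity follows from symmetry and holds under either reading of the test.

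The within-cohort day 1 to day 7 test narrows the gap without closing it: it is strong at 1 SD, about 59% powered at 0.5 SD with 27 patients, and silent about months 1 to 12. As the schedule reads, the week-1 samples for both the primary comparison and this test are not provided for.

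**What to change.** - Make the lead virologic safety analysis the fraction with a rise of at least 0.5 log10 from baseline, in each HIV cohort and pooled, at week 1 and at months 1, 3, 7 and 12. Give exact confidence limits and read them against the plan's 5%.
- Report the mean within-patient log10 change with a confidence interval, replacing the reading of a non-significant difference as no change.
- Keep the Cohort 1 versus Cohort 2 comparison as secondary, described as addressing whether HAART mitigates a rise.
- State the upper limits above, and say that one cohort of 35 cannot exclude 5%.
- State that, without an unvaccinated HIV-infected group, the estimate is a before/after change.
- Reconcile sections 6.3 and 7.5.1 with section 3.5.1.2 and Appendix 2A on HIV-1 RNA at days 1, 3 and 7, and define the baseline sample.

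**Cost.** For months 1 to 12 this is a change of analysis text with no new data, provided the screening HIV-1 RNA serves as baseline. The week-1 analysis depends on the reconciliation. The visible price is that the stated precision becomes modest.

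### The 73% power for virologic equivalence is that of one one-sided test; the plan's two-directional 10-point criterion has about 47% to 50% power with 35 per cohort

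*Combined protocol and SAP*

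**What the plan says.** Section 6.3 (Primary Virologic Safety Analysis) asks whether HIV-1 RNA behaves equivalently after vaccination in patients on HAART (Cohort 1) and patients not on HAART (Cohort 2).

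- **Type of test:** "The statistical analysis assumes that an equivalence test will be used".
- **Planning rate:** "no more than 5% of HIV-infected individuals would experience a" rise of at least 0.5 log10.
- **Criterion:** the cohorts are equivalent if the fraction with such a rise in one cohort "is within 10% of that of the other cohort". Neither cohort is named as the reference.
- **Power claim:** "Thirty-five patients are required per arm within each HIV-infected cohort, to have 73% power to document this level of equivalence".
- **Formal statement:** the 73% belongs to "a single two-group t-test of proportions with a one-sided 0.10 significance level to have 73% power to reject the null hypothesis". The null in question is non-equivalence of Cohorts 1 and 2 on this fraction.
- **Role in the design:** the first-week comparison "will be considered as the most important primary evaluation for this equivalence study and will be the basis for sample size determination".

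Neither section 6.3 nor any other part of the document describes a second one-sided test, a two one-sided tests procedure or a confidence interval for the difference.

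**The concern.** The null hypothesis of non-equivalence covers a difference beyond 10 points in either direction, so rejecting it means ruling out both. A single one-sided test rules out only one and says nothing about the other. The test that carries the 73% therefore cannot deliver the conclusion attached to it, and a procedure that can deliver it has lower power.

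Two things are at stake.

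- **If the two-sided criterion is applied,** the trial is about as likely as not to miss equivalence at the planning rate, even when the cohorts are identical. A reader relying on 73% would take that failure as a safety signal more readily than is warranted.
- **If the single test is run as written,** a large excess in the untested direction would usually be reported as equivalence. The plan does not say which direction is tested.

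**Working it through.** **Inputs, all from section 6.3**

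- n = 35 per cohort
- One-sided alpha = 0.10, so z = 1.2816
- Margin = 10 percentage points
- True rate = 5% in both cohorts. The plan gives 5% as an upper limit; equality of the two cohorts is an assumption.

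**Step 1: reproduce the plan's 73%**

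SE = sqrt(2 × 0.05 × 0.95 / 35) = 0.0521

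Power of one one-sided test = Φ(0.10 / 0.0521 − 1.2816) = Φ(1.919 − 1.282) = Φ(0.638) = 73.8%

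With a noncentral t on 68 df the result is 73.4%. The sample size for 73% power by the same formula is 35. Other readings miss the stated figure:

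| Variant | Power |
|---|---|
| One-sided alpha 0.05 | 60.8% |
| Superiority test, 5% vs 15%, one-sided 0.10 | 54.6% |
| Superiority test, 5% vs 15%, two-sided 0.10 | 40.0% |
| Continuity correction | 53.6% |

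Of the readings tried, only a single test against one margin reproduces the stated 73%.

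**Step 2: power for the two-directional criterion**

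Both one-sided tests must reject at 0.10. Equivalently, the 80% confidence interval for the difference must lie wholly inside ±10 points. At the planning SE, the observed difference must be smaller than 0.10 − 1.2816 × 0.0521 = 0.033. One patient in 35 is 2.9 points, so this amounts to a difference of at most one patient.

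Power = P(|Z| < 0.638) = 2 × 0.738 − 1 = 47.6%

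| Method | One test | Both tests |
|---|---|---|
| Normal approximation | 73.8% | 47.6% |
| t-based (both-tests figure simulated) | 73.4% | 46.9% |
| Exact binomial enumeration, Wald limits | 74.7% | 49.5% |
| Exact enumeration, Farrington-Manning | 65.9% | 32.3% |

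**Step 3: what restores 73%**

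For 73% power with both tests, each may miss with probability 0.135, for which z = 1.103:

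n = 2 × 0.05 × 0.95 × (1.2816 + 1.103)² / 0.10² = 54.03, so 55 per cohort

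For 80% power the figure is 63 per cohort. At n = 35, a margin of 12.5 points gives 73.6% by the normal approximation, but 69.4% by exact enumeration.

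**Step 4: error of the single test**

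Exact enumeration with Wald limits, true rates 15% and 5%, n = 35 per cohort:

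| Rule | Probability of declaring equivalence |
|---|---|
| Single test, excess in the untested direction | 95.3% |
| Single test, excess in the tested direction | 12.6% |
| Both tests required | 8.4% |

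**Step 5: dependence on the 5% rate (normal approximation, n = 35)**

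| True rate in both cohorts | One test | Both tests |
|---|---|---|
| 2% | 95.6% | 91.2% |
| 3% | 87.9% | 75.8% |
| 4% | 80.3% | 60.6% |
| 5% | 73.8% | 47.6% |
| 6% | 68.4% | 36.9% |

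**The case against.** The strongest reply is that the plan hides nothing: it says the test is single and one-sided, and 73% is correct for that test. That is so. The fault lies in the match between test and criterion, because section 6.3 also claims the 73% for showing that the cohorts lie within 10 points of each other, and for that claim the figure is wrong. Reading the 0.10 as the level of each of two one-sided tests does not help. The level is then acceptable, but the power is not 73%.

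Three further points stand as qualifications.

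- **The 5% is a ceiling.** At a true 3% in both cohorts, two-sided power is about 76%, so about 48% applies near the planning value. The stated 73% rests on the same 5%, however, and one-sided power rises too at lower rates.
- **The 95% error depends on direction.** Sections 8.3 and 8.4 place the greater concern about viral replication in the untreated cohort. If the single test is aimed there, a true 15% in Cohort 2 against 5% in Cohort 1 is called equivalent 12.6% of the time. Section 6.3 does not fix that direction.
- **Thirty-five per cohort has other support.** Sections 6.1 and 6.2 give separate power figures for immunogenicity, and section 1.1 lists the HIV-1 RNA question as secondary. Section 6.3 nonetheless labels this analysis primary and makes it the basis for the sample size.

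**Conclusion.** The concern holds. At the plan's own inputs, the 73% is the power of one one-sided test, while the stated equivalence criterion has about 47% to 50%, an overstatement of about 24 to 27 points. A more conservative score-type test gives about 32%. These figures assume a true rate of exactly 5% in both cohorts, a margin read as percentage points and a level of 0.10 for each test. Lower true rates narrow the gap and higher ones widen it. As written, the test named in section 6.3 cannot support a conclusion of equivalence.

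**What to change.** Amend section 6.3 in one of two ways, and replace the description of a single t-test accordingly.

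1. **Keep equivalence.** Specify two one-sided tests at 0.10 each, with equivalence declared if the 80% confidence interval for the difference in fractions lies wholly within ±10 points. Name the interval method. Restate the power at 35 per cohort as about 47% to 50% at a true rate of 5% in both, if Wald-type limits are used, and state that condition beside the figure.
2. **Keep 73%.** Restate the objective as one-directional non-inferiority and name the direction, for example that the fraction in untreated Cohort 2 is not more than 10 points above that in Cohort 1. Drop the word equivalence for this analysis.

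Both are changes of text and need no added enrolment. The cost is in the claim: option 1 admits roughly even odds of success for the comparison that set the sample size, and option 2 gives up any conclusion about the other direction. Keeping both equivalence and 73% power would take about 55 per HIV-infected cohort.

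### The first-week HIV-1 RNA analyses that section 6.3 makes primary rely on Day 3 and Day 7 samples that appear in no visit list or schedule

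*Combined protocol and SAP*

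**What the plan says.** Section 6.3 asks whether the fraction of participants with a rise of at least 0.5 log10 in HIV-1 RNA is equivalent in Cohort 1 (on HAART) and Cohort 2 (no HAART). The first of five listed comparisons, marked primary, is "Timepoint 1 Day 1 vs. Day 3 or Day 7 (immediately s/p vaccination". This first-week comparison "will be considered as the most important primary evaluation for this equivalence study and will be the basis for sample size determination". Three further uses of first-week data follow:

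- A second primary analysis: "Another primary evaluation will be based on determining the equivalence of the fractions with day 7 vs. day 1 levels" at or above the same 0.5 log10 threshold.
- A within-cohort test of the Day 1 to Day 7 change, with at least 95% power claimed for 27 participants per cohort.
- An exploratory comparison of the cohorts that includes Day 1 to Day 7.

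The cohorts count as equivalent if the fraction in one "is within 10% of that of the other cohort". With 35 per cohort, 73% power is claimed for "a single two-group t-test of proportions with a one-sided 0.10 significance level". That figure is stated to hold "at each individual time comparison--the maximum increase within the first week" and up to one year. The 5% planning rate likewise refers to an "increase in HIV-1 RNA levels within a week following vaccination or at subsequent time-points". Timepoints 2 to 5 start with "Timepoint 2 Day 1 vs. mos 1 (1mos s/p 1 vaccination" and continue at months 3, 7 and 12, each against Day 1.

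Section 7.5.1 names serial HIV-1 RNA on Days 1, 3 and 7 after the first dose as one of three things the study will be monitored for.

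**The concern.** The statistical section and the schedule contradict each other on the virologic evaluation that 6.3 ranks highest. If the schedule is complete, the first-week comparison of treated and untreated participants cannot be reported, nor can the within-cohort Day 1 to Day 7 change. A reader of 6.3 and 7.5.1 would nevertheless believe that acute viral rises were being measured.

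This matters because the protocol's risk section (8.3) names upregulation of HIV replication as a potential risk, of more concern without antiretroviral therapy. The background (1.2.5) also reports that rises seen after other vaccines were in several studies transient. A sample at about one month may not show what a first-week sample was meant to catch.

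**Working it through.** **1. The stated power figures follow from their inputs.** Inputs from 6.3: n = 35 per cohort, rate 0.05 in both, margin 0.10, one-sided alpha 0.10.

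- SE = sqrt(2 × 0.05 × 0.95 / 35) = 0.0521.
- Power = Φ(0.10/0.0521 − 1.2816) = Φ(0.638) = 0.738, against the stated 73%. A noncentral t with 68 degrees of freedom gives 0.734.
- Within-cohort paired t-test, n = 27, effect 1 SD, two-sided alpha 0.025: 99.6%, consistent with the claim of at least 95%.

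The arithmetic is sound. The question is whether the data it describes are scheduled.

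**2. Where a Day 3 or Day 7 draw could appear.**

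| Place | What it lists |
|---|---|
| Precis, Study Design | Months 0, 1, 2, 3, 6, 7, 12, then every 6 months |
| 3.5.1 | Vaccine visits at months 0, 2, 6 |
| 3.5.2 | Months 1, 3, 7, 12; HIV-1 RNA listed |
| 3.5.3 | Months 18 to 48; HIV-1 RNA listed |
| Appendices 2A and 2C | Screening, Mo 0 D1, then months 1, 2, 3, 6, 7, 12; no Day 3 or Day 7 column |
| Appendix 6 | Research blood timepoints, all in months |
| Appendix 11 | 7 visits in the first year |

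Months 0, 1, 2, 3, 6, 7 and 12 make seven visits, so the Appendix 11 count leaves no room for another. Section 3.5 places all study visits at the NIH Clinical Center, and no off-site draw is described. Section 7.5.1 mentions Days 1, 3 and 7 but is a monitoring statement and schedules nothing.

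**3. Earliest scheduled value after dose 1.** Taking a month as 30 days (assumption), month 1 ± 14 days is day 16 to day 44.

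**4. What is lost and what remains.** Scheduled first-week draws: 0 of 2, for 2 × 35 = 70 planned participants. Analyses without scheduled data: 2 primary + 1 within-cohort + 1 exploratory limb = 4. Timepoints 2 to 5, four of the five listed, keep their follow-up draws.

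**5. The Day 1 reference.** Timepoints 2 to 5 also need a Day 1 value. HIV-1 RNA is not listed for month 0 in 3.5.1.2, Appendix 2A or Appendix 2C. The month-0 tubes in Appendix 2C sum to 10 + 60 + 10 + 10 + 18 + 20 = 128.0 ml, the printed total, without the 6.0 ml tube shared by HIV-1 RNA and CD4. At month 1 the sum is 3 + 6 + 4 + 60 + 10 + 10 = 93.0 ml, the printed total with that tube. The blank at month 0 is therefore not a fault in table extraction. Section 3.5.1.2 omits HIV-1 RNA at months 2 and 6, where Appendix 2A marks it. A screening value does exist (2.2.1.18), taken 1 to 14 days before dose 1. If it were the reference, the interval to month 1 would run from 16 + 1 = 17 to 44 + 14 = 58 days.

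**6. How far the 73% carries over.** It holds for later comparisons at the plan's 5% rate. If ordinary drift over a longer interval raised the rate to 10% in both cohorts (an assumption, for range only), SE = sqrt(2 × 0.10 × 0.90 / 35) = 0.0717 and power = Φ(0.10/0.0717 − 1.2816) = 0.54.

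**The case against.** The strongest reply is that little of the trial depends on this. Section 1.1 lists the HIV-1 RNA question as a secondary objective, and 5.2 makes immunogenicity the primary focus. Sections 6.1 and 6.2 justify 35 per cohort separately: recomputation gives 94.4%, 90.1% and 99.6%, against the stated 94%, 90% and 99%. The accrual stopping rule in 6.7 needs no first-week sample. All of that stands and limits the consequence. It does not remove the contradiction, because 6.3 itself calls the first-week comparison primary and most important.

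Stronger readings are tempting but not supported:

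- **That first-week samples were never drawn.** The public documents lack the consent pages and say nothing about actual collection. They show only that no visible schedule contains these draws.
- **That no Day 1 HIV-1 RNA exists.** It is unlisted in three places, and the tube volumes agree with that. But 3.5.1.2 lists a month-0 CBC and CD4 count that Appendix 2A leaves blank, so the month-0 lists already disagree. The pregnancy-test requirement in 11.1.5 does not help either way, since a screening test could satisfy it for dose 1.
- **That the 73% or the sample size collapses.** The plan extends both the 5% rate and the 73% to later timepoints. Whether the 10% margin must be met on both sides is a separate question from the missing draws.
- **That month 1 should become the lead evaluation.** That would be a different question from an acute first-week one, and removing the contradiction does not require it.

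**Conclusion.** The plan is wrong as written on this point. Four analyses in 6.3, two of them labelled primary, and the first-week monitoring in 7.5.1 depend on Day 3 or Day 7 HIV-1 RNA values that no visible schedule provides. The first scheduled post-dose value falls at about day 16 to 44. The loss is confined to first-week virologic conclusions: the between-cohort comparisons at months 1, 3, 7 and 12 keep their follow-up draws, and immunogenicity is unaffected. The missing month-0 HIV-1 RNA entry and the disagreement at months 2 and 6 are related, lesser mismatches on which the conclusion does not rest. It assumes only that the visible schedules are the operative ones.

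**What to change.** Reconcile 6.3 and 7.5.1 with section 3.5 and Appendix 2, including whether HIV-1 RNA is drawn at months 0, 2 and 6.

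If first-week samples are or were collected, show them in the visit lists and in Appendices 2A and 2C. Only schedule text changes.

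If they are not:

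1. Remove the Day 3 and Day 7 analyses and the Day 7 power claim from 6.3.
2. State that first-week rises in HIV-1 RNA are not assessed, and bring 7.5.1 into agreement with the samples available.
3. Keep Timepoints 2 to 5 as listed, and say that the 73% applies to them only under the 5% assumption.
4. If no Day 1 sample exists, name the screening value as the reference.

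Date the change. This version is from January 2019, after the IND was withdrawn in April 2018, and accrual status is not stated. If data have been collected, label the change post hoc.

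No new samples are needed. The cost is that no first-week virologic claim can be made. If screening is the reference, the interval to month 1 is longer and variable (17 to 58 days), so some rises may be drift.
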